#### Phase 3: Health Economic evaluation

The resources needed to design and develop the DVD intervention will be recorded during phase 1. During the trial we will also record all resources required to provide the interventions in the DVD and the 'face-to-face' physiotherapy groups. Information will also be collected on all asthma-related healthcare costs for the 1-year follow up period.

#### 3.1 TRIAL OUTCOME MEASURES

Outcome measures will be between-group and within-group changes from baseline to the end of the study (12 months).

The primary outcome will be an analysis of the between-group (Intention-To-Treat (ITT)) change in asthma-specific health status (AQLQ (short version) score).

Secondary outcome measures will be: Asthma Control Questionnaire score; Lung function (FEV1, FEV1/FVC ratio, PEFR); Fraction of exhaled nitric oxide; Health status (EuroQOL); Anxiety and depression scores (HAD questionnaire; Hyperventilation (Nijmegen) questionnaire; Oral corticosteroid courses; Bronchodilator use; Asthma related health resource use; Smoking status; Cost effectiveness/utility; Patient reported process evaluations (questionnaires) and estimates of adherence (use of exercises).

#### 4. SELECTION AND ENROLEMENT OF SUBJECTS

#### 4.1 SCREENING AND PRE-REGISTRATION / RANDOMISATION EVALUATIONS

We plan to recruit 585 patients (234 in each of the DVD and 'usual care' arms and 117 in the 'face-to-face' physiotherapy arm) from 20 general practice centres, aiming for up to 30 subjects per GP centre. All general practices now have 'asthma registers' of all patients with currently active asthma, as this is a requirement for payment under the NHS Quality and Outcomes Framework system. Patients on the practice asthma register meeting the inclusion criteria below and who have received prescriptions for any asthma medication in the previous 12 months will be identified from the practice computer records by practice staff. A mail merge will be performed at the practice sending out a study invitation letter with full information. People wishing to have more information about the trial will be provided with contact telephone numbers to enable them to speak to study staff at the University of Southampton Clinical Trials Unit (UoSCTU), or encouraged to talk to their GP. People potentially interested in study participation will be asked to provide contact details, to complete the mini-AQLQ (Asthma Quality of Life Questionnaire (23) and to

BREATHE Page 17 of 35 Protocol v6 01-08-2014

return these to the Study Co-ordinator in a pre-addressed stamped envelope. Only those with impaired health status (AQLQ score <5.5) will be recruited, as lack of impairment in health status does not allow 'room for improvement' in the primary outcome measure. In our previous work and other studies, 75% or more or people with asthma treated in the community have impaired health status.

Subjects meeting the entry criteria will be given an appointment to see the study nurse for the baseline visit, which will occur at the subject's general practice at a mutually convenient time. Any questions about the study will be answered, and informed consent obtained. A study nurse will perform the baseline assessment. This will consist of:

- Facilitating subject completion of validated questionnaires: Disease-specific health status (AQLQ) (23), Nijmegen hyperventilation questionnaire (24), Generic health status (EuroQOL, EQ-5D) (25); anxiety and depression scores (HAD questionnaire) (26), Asthma control questionnaire (ACQ) (27).
- Clinical details: Smoking status, asthma history, co-morbidities, medication, and exacerbation frequency.
- Physiological measurements: Spirometry (FEV1, FEV1/FVC ratio, PEFR), measured with standardized calibrated portable spirometer; Fraction of exhaled nitric oxide (FENO), measured with Aerocrine Mino portable monitor.

If a clinical assessment of potentially dangerous or unstable asthma is made by the trained study nurse, the subject will not enter the study but will be referred urgently back to their usual primary care asthma clinician. Participants who score greater than or equal to 16 in the HADs Questionnaire will be sent a letter from the trial team advising that they may wish to discuss this with their GP. When informed consent has been provided and the baseline assessment completed, the study nurse will telephone UoSCTU for randomisation (or use the web based system when in place). Those randomised to 'usual care' will be informed that they will be posted questionnaires in 3 and 6 months' time to complete and return to the study co-ordinator, and that a final assessment visit will be scheduled for 12 months post randomisation. Contact information will be provided. Those randomised to the DVD intervention will be provided with the written instructional material developed in phase 1 and the DVD. For those who do not have a DVD player at home, an inexpensive DVD player will be provided; it is however anticipated that most people will have access to one of these media players. Subjects will be given information that they will be posted questionnaires in 3 and 6 months to complete and return to the coordinator, and that a final assessment visit will be scheduled for 12 months. Contact information will be provided. For those randomised to the 'face-to-face' physiotherapy arm, they will be informed that they will receive 3 short sessions of contact with a respiratory physiotherapist for breathing retraining. These sessions will be approximately 30-40 minutes long and will occur at roughly 2 weekly intervals following randomisation. The retraining can occur at either the GP surgery, clinic setting or the patient's home according to convenience and preference. The content of the retraining programme

BREATHE Page 18 of 35 Protocol v6 01-08-2014

will be based on those shown to be effective in recent studies (16-18), and similar to the content of the DVD intervention.

Subjects will be informed that they will be posted questionnaires in 3 and 6 months time to complete and return to the study co-ordinator, and that a final assessment visit will be scheduled for 12 months post randomisation. Contact information will be provided for all three randomisation groups.

#### 4.2 INCLUSION CRITERIA

- Full practice registration for a minimum of 12 months prior to enrolment
- Age 16-70 yrs
- Physician diagnosed asthma in medical record
- ≥1 anti-asthma medication prescription in the previous year (determined from the physician prescribing records)
- Impaired asthma-related health status (Asthma Quality of Life Questionnaire score of <5.5)

- Informed consent

#### 4.3 EXCLUSION CRITERIA

- Asthma judged at the baseline assessment to be dangerously unstable and in need of urgent medical review (if unstable asthma is found, the patient will be referred back to usual primary care clinician for review)
- Documented diagnosis of Chronic Obstructive Pulmonary Disease (COPD) with a FEV1 percent predicted of 60% or lower

We aim to allow broad entry criteria (with inclusion of smokers, and not insisting on physiological demonstration of reversible airflow obstruction) in order to allow generalisability of research findings to mild-to-moderate UK asthma populations treated in primary care NHS practice.

#### 4.4 REGISTRATION / RANDOMISATION PROCEDURES

Patients who meet the eligibility criteria for the study as determined by the inclusion and exclusion criteria will be registered with the University of Southampton Clinical Trials Unit by telephone by contacting the following number:

Randomisation [contact] Monday – Friday: 09.00 to 17.00hrs

All subjects will undergo screening investigations as detailed in section 4.1.

#### 4.5 WITHDRAWAL CRITERIA

Participants are free to withdraw at any time without giving any reason.

BREATHE Page 19 of 35 Protocol v6 01-08-2014

Data collected up to the time of withdrawal may continue to be used in the study unless the participant expressly withdraws consent to the continued use of such data.

[figure not shown]
#### 5. STUDY INTERVENTION

#### 5.1 TREATMENT ARMS

We propose a prospective evaluation of a physiotherapy breathing retraining programme (already shown to be effective in face-to-face contact) delivered in a new DVD format. If effective, this could be used in routine NHS asthma care. The DVD breathing instruction programme will be developed in phase 1 of the project. In the subsequent randomised controlled trial (phase 2), we will assess the effectiveness of this DVD as adjuvant treatment for asthmatic adults with asthma-related health status impairment (AQLQ <5.5) despite pharmacotherapy. Consenting subjects will be randomly assigned to

- Arm A: Receipt of the DVD, (plus supporting written material)
- Arm B: Usual care
- Arm C: 3 sessions of 'face-to-face' physiotherapy breathing instruction (plus supporting written material)

In all 3 arms, no attempt will be made to change the standard asthma care provided in the practice.

#### 6. ADVERSE EVENTS AND REPORTING

#### 6.1 **DEFINITIONS**

Adverse Event (AE): any untoward medical occurrence in a patient or clinical trial subject which does not necessarily have a causal relationship with trial treatment or participation.

Serious Adverse Event (SAE): any untoward occurrence that:

- · Results in death
- Is life-threatening refers to an event in which the subject was at risk of death at the time of the event; it does not refer to an event which hypothetically might have caused death if it were more severe

- Requires hospitalisation, or prolongation of hospitalisation
- Results in persistent or significant disability or incapacity

Medical judgement should be exercised in deciding whether an AE is serious in other situations. Important AE that are not immediately life-threatening or do not result in death or hospitalisation but may jeopardise the subject or may require intervention to prevent one of the other outcomes listed in the definition above, should also be considered serious.

**Suspected Unexpected Related Adverse Event:** any serious adverse event thought to have resulted from administration of any of the research procedures (related) and where the type of event is not listed in the protocol as an expected occurrence (unexpected).

#### 6.2 RELATEDNESS

The assignment of the relatedness to trial treatment of any serious event should be made by the investigator responsible for the care of the subject using the definitions in the table below.

If any doubt about the causality exists the local investigator should inform the UoSCTU who will notify the Chief Investigator. Other clinicians may be asked for advice in these cases.

In the case of discrepant views on causality between the investigator and others, all parties will discuss the case. In the event that no agreement is made, the Ethics Committee will be informed of both points of view.

Relationship	Description			
Unrelated	There is no evidence of any related relationship			
Unlikely	There is little evidence to suggest there is a related relationship (e.g. the event did not occur within a reasonable time after the research procedure). There is another reasonable explanation for the event (e.g. the subject's clinical condition, other concomitant treatment).			
Possible	There is some evidence to suggest a related relationship (e.g. because the event occurs within a reasonable time after the research procedure). However, the influence of other factors may have contributed to the event (e.g. the subject's clinical condition, other concomitant treatments).			
Probable	There is evidence to suggest a related relationship and the influence of other factors is unlikely.			
Definitely	There is clear evidence to suggest a related relationship and other possible contributing factors can be ruled out.			

#### 6.3 REPORTING PROCEDURES

All adverse events should be reported. Depending on the nature of the event the reporting procedures below should be followed. Any questions concerning

adverse event reporting should be directed to the UoSCTU in the first instance. A flowchart will be provided to aid in the reporting procedures.

#### 6.3.1 Pre-existing Conditions

A pre-existing condition should not be reported as an AE unless the condition worsens by at least one CTCAE grade during the trial. The condition, however, must be reported in the pre-treatment section of the CRF, if symptomatic at the time of entry, or under concurrent medical conditions if asymptomatic.

#### 6.3.2 Non serious Adverse Events

All adverse events that may be related to the study will be recorded in the relevant case report form and Adverse Event form and sent to the UoSCTU within one month of the form being due. As adults on average see their GP approximately 5 times per year for a variety of routine and unscheduled appointments (e.g. for medication review, self-limiting minor illnesses and long-term conditions unrelated to asthma), many medical encounters are of no relevance to the study. Events that will be recorded include any judged by the study nurse to be possibly related to the study. In particular, all medical encounters related to the following medical areas or symptoms will be recorded in the Adverse Events form:

**Psychological morbidity:** any events relating to anxiety, depression or mood disorders

**Respiratory morbidity**: any events relating to breathing or chest symptoms

**Musculoskeletal, Abdominal and chest pain:** any events relating to pain in these systems unless known to be associated with an unrelated pre-existing condition.

The study nurses are advised to record any event for which there is uncertainty as to whether it is study related or not, and to discuss with the local PI or CI.

#### 6.3.3 Serious Adverse Events

All SAEs (including those that are expected and related) will be reported within 24 hours of the local site becoming aware of the event. The SAE form asks for nature of event, date of onset, severity, corrective therapies given or action taken, outcome and relatedness (i.e. unrelated, unlikely, possible, probably, definitely). The responsible centre Principal Investigator will assign the relatedness and expectedness of the event. Additional information will be provided as soon as possible if the event has not resolved at the time of reporting.

#### 6.3.4 Reporting Details

An SAE form should be completed for all SAEs and faxed to the UoSCTU within 24 hours.

Complete the SAE form & fax or email a scanned copy of the form with as many details as possible to the UoSCTU together with anonymised relevant treatment forms and investigation reports.

BREATHE Page 22 of 35 Protocol v6 01-08-2014

Or

Contact the UoSCTU by phone for advice and then fax or email a scanned copy of the completed SAE form.

The UoSCTU will notify the REC of all SUSARs occurring during the trial within 15 days. All investigators will be informed of all SUSARs occurring throughout the trial.

Local Investigators will report any Unexpected and Related Serious Adverse Events and / or SAEs as required by their Local Research & Development Office.

#### 6.3.5 Follow Up and Post-study Serious Adverse Events

The reporting requirement for SAEs affecting subjects applies for all events occurring up to the end of the last treatment. All unresolved adverse events should be followed by the local investigator until resolved, the participant is lost to follow-up, or the adverse event is otherwise explained. At the last scheduled visit, the investigator should instruct each participant to report any subsequent event(s) that the participant, or the participant's general practitioner, believes might reasonably be related to participation in this study. The investigator should notify the University of Southampton Clinical Trials Unit of any death or adverse event occurring at any time after a subject has discontinued or terminated study participation that may reasonably be related to this study.

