#### **Duration of Intervention:**

- Face-to-face physiotherapy Arm: 3 sessions lasting 30 minutes at approximately 2 weekly intervals
- DVD For use by participants at own home as convenient

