#### **Control Group:**

Usual GP care for adults with asthma

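### Section 6.3.5 ties SAE reporting to the end of treatment, an end point that differs by arm and contradicts the schedule and section 6.3.3

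*Protocol*

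**What the plan says.** Protocol section 6.3.5 sets the length of SAE reporting: "The reporting requirement for SAEs affecting subjects applies for all events occurring up to the end of the last treatment". No date, week or visit is attached to that end point. The same section then asks for later events, at any time after participation has ended, but only those that may be related to the study.

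The arms are described as follows:

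- **Face-to-face** (synopsis, Duration of Intervention): "Face-to-face physiotherapy Arm: 3 sessions lasting 30 minutes at approximately 2 weekly intervals".
- **DVD** (same place): "For use by participants at own home as convenient".
- **Usual care** (synopsis, Control Group): "Usual GP care for adults with asthma". Section 5.1 adds: "In all 3 arms, no attempt will be made to change the standard asthma care provided in the practice".

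Other parts of the protocol point to a longer, common period. The Schedule of Observations and Procedures marks adverse events at baseline, at the physiotherapy sessions and at 3, 6 and 12 months. It also marks a medical notes review at 12 months. Apart from the physiotherapy sessions, none of these is limited to an arm. Section 6.3.3 requires every SAE to be reported within 24 hours of the site learning of it, and states no closing date. Section 3.1 measures outcomes over 12 months, and section 7.1 ends the trial at the last final assessment or withdrawal.

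**The concern.** An end-of-treatment cut-off works when every arm has a treatment course of known and similar length. Here one arm has a short fixed course, one has a resource kept at home for use at will, and one has nothing that the trial supplies. A site that applies section 6.3.5 as written would stop SAE reporting early for face-to-face participants and would have no rule for the others.

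Two things are at stake. First, the Data Monitoring and Ethics Committee and the final report could receive SAE counts gathered over different lengths of time in different arms. Second, an SAE judged unrelated that occurs between the third session and month 12 need not be reported under 6.3.5: it falls after the cut-off, and the later duty covers only possibly related events once participation is over. A missing site report of this kind cannot be recovered by an analysis plan.

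**Working it through.** **Step 1. The cut-off in each arm, read literally**

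| Arm | Last trial treatment | SAE window under 6.3.5 |
|---|---|---|
| Face-to-face | Third session | Ends early in follow-up |
| DVD | No end stated | Cannot be determined |
| Usual care | No trial treatment | No anchor |

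**Step 2. Length of the face-to-face window**

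Three sessions have two gaps of about 2 weeks, so the last session is 2 × 2 = 4 weeks after the first. The protocol gives no interval from randomisation to the first session. Assume 0 to 4 weeks:

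- shortest: 0 + 4 = 4 weeks, 4/52 = 7.7%
- longest: 4 + 4 = 8 weeks, 8/52 = 15.4%

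So 44 to 48 of the 52 weeks (85% to 92%) would lie outside the window.

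**Step 3. What this could do to counts**

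The arm sizes come from the Summary in section 8.1 and reproduce exactly with 10% dropout: 210/0.9 rounds up to 234 (twice), 105/0.9 rounds up to 117, and 234 + 234 + 117 = 585.

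The protocol gives no SAE risk. The annual risks below are assumptions, spread evenly over the year and equal in all arms. Expected SAEs = arm size × annual risk × weeks/52.

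| Assumed annual risk | Face-to-face (n=117), 4-8 weeks | Face-to-face (n=117), 52 weeks | DVD or usual care (n=234), 52 weeks |
|---|---|---|---|
| 2% | 0.18-0.36 | 2.34 | 4.68 |
| 5% | 0.45-0.90 | 5.85 | 11.7 |
| 10% | 0.90-1.80 | 11.7 | 23.4 |

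If sites used 6.3.5 for face-to-face participants and a full year for usual care, equal true risk would appear as a per-participant ratio of 4/52 to 8/52, about 0.08 to 0.15. This is the extreme of a literal reading and not a forecast of what sites would do.

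**Step 4. The other rules beside 6.3.5**

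- *Schedule:* adverse events are collected to month 12 in all arms. Section 6.3.5 would have the SAE duty end before that in one arm.
- *Section 6.3.3:* all SAEs, including those classed as unrelated, with no time limit. Section 6.3.5 imposes a limit on the same duty.
- *Second part of 6.3.5:* starts when participation ends and is filtered by relatedness. A face-to-face participant past the third session is still in the trial until the 12-month visit, so this part does not bridge the interval.

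The first two cannot both hold together with the opening sentence of 6.3.5.

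**The case against.** The strongest reply is that one badly worded sentence stands against several that imply a common 12-month period: the schedule, section 6.3.3, the references in section 6.3.4 to unexpected related events arising during the trial, and the end-of-trial definition in section 7.1. Usual care is also listed among the treatment arms in section 5.1 and continues in all three, so a reader could take treatment to last 12 months for everyone. This stands in part. It shows that year-long collection was probably intended, but 6.3.5 is the only text that states how long SAE reporting lasts, and it says something else.

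Several stronger readings are tempting, and the documents do not support them:

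- **That SAEs cannot be compared between arms.** The 12-month adverse-event row, the notes review and section 6.3.3 apply to every arm. Comparability is at risk only so far as sites follow 6.3.5.
- **That late respiratory admissions would be lost.** Section 6.3.2 records medical encounters for breathing or chest symptoms, and the health economic evaluation in section 7 collects all asthma-related NHS use, including secondary care, for the year.
- **That section 6.3 contradicts section 6.3.2.** Section 6.3 says "All adverse events should be reported" and section 6.3.2 narrows this to events that may be study-related, but the next sentence of 6.3 refers the reader to the procedures below it. This is a loosely worded general rule followed by its detail.
- **That a usual-care event can never be study-related.** Section 6.1 ties relatedness to any research procedure, and usual-care participants undergo spirometry, exhaled nitric oxide measurement and questionnaires.
- **That events noted at physiotherapy visits must be listed apart.** Extra contact is inherent in that arm, and how to present such events is an analysis choice that an SAP may settle.

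It is also fair to say that SAEs are not a listed outcome and that the protocol states no between-arm SAE comparison.

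**Conclusion.** The sentence is wrong as written and should be corrected. It contradicts the schedule and section 6.3.3, and its end point comes early in one arm, is undefined in the second and does not exist as a trial treatment in the third. If it is followed, SAE counts may not be comparable between arms, and SAEs judged unrelated after the last physiotherapy session need not be reported.

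The face-to-face window of about 4-8 of 52 weeks (8-15%) rests on the assumed 0-4 weeks to the first session. The expected counts rest further on assumed SAE risks. The contradiction itself needs neither assumption. The effect on monitoring and on the final report is inferred, and depends on how sites resolve the conflict. The primary AQLQ analysis and the sample size are not affected.

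**What to change.** Reconcile section 6.3.5 with the schedule and section 6.3.3 by stating one window that does not depend on arm: SAEs are reported from randomisation to the 12-month final assessment in all three arms, regardless of relatedness. Keep the duty limited to possibly related events for the period after participation ends.

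The cost is a wording change in the protocol and some additional SAE forms. The contacts at 3, 6 and 12 months and the notes review are already scheduled.
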